### 7.7.3. Vital Signs

Descriptive statistics for each vital sign (e.g. systolic blood pressure, diastolic blood pressure, pulse rate, body temperature, respiratory rate, height, weight, body mass index) will be summarized at scheduled visits. Summaries will include actual values and changes from baseline. A summary table of potentially clinically significant shifts in vital signs will also be generated separately for pediatric patients (<18 years old) and adult patients.

For any patient <18 years old at screening, the modified z-score will be calculated for height, weight and body mass index (BMI) according to the CDC growth chart. A summary table of descriptive statistics of z-scores by visits and treatment arm will be summarized. A tabular summary of the proportion of patients with z-scores at various cut-points (e.g. ≥+/- 2 SD) will also be summarized as well.

A separate listing of vital sign data will be generated. Per patient plots of z-scores over time for those patients <18 years old at screening will also be generated.

### 7.7.4. Physical Examinations

During the study, full physical examinations and abbreviated physical examinations will be conducted throughout the study. If any abnormalities are observed during these physical exams, then this will be recorded on the adverse event form.

A separate listing per patient will be generated to display the date and time of the physical exam.

### 7.7.5. Electrocardiogram

Electrocardiogram (ECG) parameters include rhythm, ventricular rate, PR interval, QRS duration, QT interval, and QTc interval. Corrected QT interval (QTc), if not collected, will be calculated using the Fridericia's correction formula.

Fridericia's cube-root corrected QT: QTcF (ms) = QT (ms) 
$$\times \sqrt[3]{\frac{HR(bpm)}{60}}$$
.

The number and percentage of patients with normal, abnormal, and clinically significant abnormal results at baseline and each timepoint will be summarized.

For electrocardiogram parameters, these will be summarized using descriptive statistics for actual values and for changes from baseline by scheduled time of evaluation.

Baseline, post baseline maximum QTcF and post baseline maximum change from baseline in QTcF during the study will be summarized with descriptive statistics. The incidence of notable ECG changes from baseline in maximum absolute QTcF, intervals (<=450, >450, >480, and >500 ms) over all post-treatment evaluations, as well as in QTcF, maximum changes from baseline (<=30 ms, >30-60 ms and >60 ms) over all post-treatment evaluations will be summarized.

A listing of all ECG data will be provided.

### 7.8. Anti-Drug Antibody

The number and associated percentage of patients who are ADA positive at baseline and at any post-baseline visit will be summarized by treatment group. A listing of patients with positive ADA assay results will be provided as well as a listing of all ADA results.

# 8. CHANGES TO PLANNED ANALYSES

Below is a summary of changes in the Statistical Analysis Plan (SAP) version 2.0 which differ from SAP version 1.0 with corresponding rationale of why the change had been made.

Summary of Changes	Rationale
List and order of secondary endpoints are modified (Section 3.2 and Section 5.6).	The change to the list of secondary endpoints is made to align with protocol amendment 2. Additionally, additional results from ALN-GO1-001 was evaluated to change the order of secondary endpoints to mitigate the risk
Changes to sensitivity analysis to primary endpoint (Section 7.1):  Replace the initially planned sensitivity analysis with 2 sensitivity analyses to evaluate the assumption of steady state from month 3 to month 6  Remove per-protocol analysis	The initially planned sensitivity analysis evaluates an endpoint of percent change from baseline at Month 6, which differs from the primary endpoint. Furthermore, this analysis is covered by the newly added sensitivity analysis.  New sensitivity analyses are added to evaluate the sensitivity to the estimated treatment effect of the primary analysis by the assumption of lumasiran reaching steady state of the treatment effect at Month 3 and maintained through Month 6.  Per-protocol analysis, though it helps address a question related non-compliance, does not provide additional evidence to efficacy.
Secondary endpoint (Section 3.2)  Percent change in 24-hour urinary oxalate: creatinine ratio (value/ULN) from baseline to Month 6	The endpoint is modified because the 24h urinary oxalate: creatinine ratio upper limit of normal for ages 6 years and older is being extrapolated from the healthy adult population assessed with the validated PD assay. This extrapolation is supported by published data that suggest oxalate: creatinine in children 6 and above is similar to adults.
ULN value for 24-hour urinary oxalate corrected by BSA is defined in Appendix	The ULN for the assay has been determined based on 100 samples from healthy normal volunteers. Refer to Biomarker white paper for details. The initial ULN value quoted is ULN for Clinical Diagnostic Assay from hence is not applicable and removed.
Plasma Oxalate Analysis Set is added for the analysis of plasma oxalate endpoints	The LLOQ of the plasma oxalate assay is 5.55 µmol/L. Due to the inability of quantify oxalate level below LLOQ by the assay, patients with baseline plasma oxalate level measured near at LLOQ are excluded from the analysis to ensure the meaningful reduction can be evaluated for the study population.
Add SAE and AE subgroup analyses for the double blinded period	These safety analysis by Age, Race, Gender, Region, eGFR are aligned with ISS

Summary of Changes	Rationale
Other edits throughout	To improve clarity

# APPENDIX A. UPPER LIMIT OF NORMAL FOR 24-HOUR URINARY OXALATE CORRECTED FOR BSA

To establish accurate and reproducible reference ranges of oxalate and glycolate levels in urine and plasma of healthy subjects, human urine and plasma samples from healthy male and female subjects were procured from BioIVT (formerly Bioreclamation IVT, Westbury, NY, USA), a commercial provider of biological samples. Of these samples, 24-hour urine samples were available from 100 healthy adults. Samples were processed and analyzed for oxalate using Quantitative PD Assay validated at \_\_\_\_\_\_.

The ULN, based on these samples, for 24-hour urinary oxalate corrected for BSA is estimated to be 0.514 mmol/24hr/1.73m^2. Details for sample collection and analysis and statistical method for ULN determination will be available from the white paper for Urinary and Plasma Levels in Healthy Subjects.

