4. SELECTION AND WITHDRAWAL OF PATIENTS

4.1. Inclusion Criteria

Patients are eligible to be included in the study if all the following criteria apply:

Age

1. Age 6 years or older.

Patient and Disease Characteristics

2. Documentation or confirmation of PH1 as determined by genetic analysis prior to randomization.
3. Mean 24-hour urinary oxalate excretion from the first 2 valid 24-hour urine collections is ≥ 0.70 mmol/24h/1.73m²
4. If taking pyridoxine (vitamin B6) for the treatment of PH1, must have been on stable regimen for at least 90 days before randomization, and willing to remain on this stable regimen for 12 months from first study drug administration.

Informed Consent

5. Patient is able to understand and is willing and able to comply with the study requirements and to provide written informed consent. In the case of patients under the age of legal consent, the legal guardian(s) must provide informed consent and the patient should provide assent per local and national requirements.

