#### **5.4.** Baseline Definitions

### Baseline definitions applied to double-blind (DB) period:

For 24-hour urine PD parameters, baseline will be defined as the median of all valid 24-hour urine PD parameters collected prior to the first dose date/time of study drug (lumasiran or placebo). Baseline for other PD parameters will use the mean of all measurements collected prior to the first dose date/time of study drug (lumasiran or placebo).

For other parameters, baseline is defined as the last non-missing value prior to the first dose date/time of the study drug (lumasiran or placebo), unless otherwise specified. The baseline value for any measurements with multiple values at a visit (e.g. ECGs, height and weight for patients <18 years old) will be defined as the mean of the latest values collected prior to the first dose date/time of study drug.

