### **Baseline definitions applied to During Lumasiran Treatment:**

For patients randomized to lumasiran, baseline as defined above for the double-blind period will be used.

For patients randomized to placebo who took at least one dose of lumasiran in the extension period, baseline for all parameters [except for 24-hour urine PD parameters] will be defined as above but the date of the first dose date/time of study drug will be the first date/time of lumasiran dose. For 24-hour urine PD parameters, the baseline will be defined as the median of all valid assessments at month 6. If the subject does not have two valid 24-hour urine PD assessments at month 6, then the baseline will be calculated based on the latest three valid 24-hour urine PD collections prior to the first dose date/time of lumasiran.

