# **5.6.** Multiple Comparisons/Multiplicity

The family-wise Type I error control for the primary and secondary endpoints will be achieved by the gatekeeping testing strategy. Once the primary hypothesis testing is statistically significant at a 2-sided 0.05 significance level, the secondary endpoints will be tested in the following hierarchical order.

- 1. Absolute change in 24-hour urinary oxalate corrected for BSA from baseline to Month 6
- 2. Percent change in 24-hour urinary oxalate: creatinine ratio from baseline to Month 6
- 3. Percent change in plasma oxalate from baseline to Month 6
- 4. Proportion of patients with 24-hour urinary oxalate levels at or below 1.5xULN at Month 6
- 5. Proportion of patients with 24-hour urinary oxalate levels at or below ULN at Month 6
- 6. Absolute change in plasma oxalate from baseline to Month 6

Only if the comparison is significant at a 2-sided 0.05 significance level will the next endpoint in the hierarchy be formally tested; if a given comparison is not significant at a 2-sided 0.05 significance level, the subsequent tests will be performed, and the results will be summarized, but statistical significance will not be inferred.

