# 7.2. Secondary Endpoints

For secondary endpoints assessed to Month 6, the analysis will compare randomized arms (lumasiran vs. placebo) using the Full Analysis Set. During the Double-Blind Period, data will be collected during Screening, Day 1 and Months 1, 2, 3, 4, 5 and 6 with the exception of eGFR which is also collected at Week 2. To control for type I error, the primary and selected secondary endpoints will be tested in a hierarchical order as described in Section 5.6.

Absolute change from baseline in 24-hour urinary oxalate corrected for BSA will be analyzed using an MMRM model as specified for the primary endpoint. The percent change in 24-hour urinary oxalate: creatinine ratio, the percent change and the absolute change in plasma oxalate from baseline to Month 6 will also be analyzed using a similar MMRM model to the primary endpoint with the exception being that the baseline variable will be the baseline value of the corresponding endpoint.

For the two plasma oxalate related endpoints, a separate enriched analysis set of patients (i.e., Plasma Oxalate Analysis set) will be used. The plasma oxalate analysis set is defined as those patients who received any amount of study drug and have a baseline plasma oxalate level  $\geq$  1.5\*LLOQ. The LLOQ of the plasma oxalate assay is 5.55 µmol/L. Because it is not

possible to quantify plasma oxalate levels below LLOQ using the assay, patients with baseline plasma oxalate levels near the LLOQ (i.e. <1.5\*LLOQ) are excluded from the analysis to ensure that meaningful reductions in plasma oxalate can be evaluated for the study population.

For binary endpoints, i.e., the proportion of patients with 24-hour urinary oxalate  $\leq$ 1.5 ULN and  $\leq$  ULN at Month 6 the number and associated percent of patients who met each threshold at Month 6 will be presented by treatment arm. Refer to Appendix A for the value of ULN. Binary endpoints will be analyzed using a Cochran-Mantel-Haenszel (CMH) test stratified by baseline urinary oxalate ( $\leq$ 1.70 mmol/24hr/1.73m² vs. >1.70 mmol/24hr/1.73m²). The odds ratio with the corresponding 95% confidence interval and associated p-value will be presented. In addition, the differences in proportion of responders and corresponding 95% confidence interval using the Newcombe method based on the Wilson score will also be presented.

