For continuous endpoints (including eGFR), descriptive statistics will be generated by treatment arm. LS Mean (+/- standard error) by treatment arm will be plotted for continuous PD endpoints. Spaghetti plots will also be generated for all continuous endpoints.

Table 2: Analysis of Secondary Endpoints to Month 6^

Endpoints	Statistical Method	Analysis Population
Absolute change in 24-hour urinary oxalate to Month 6	MMRM	Full Analysis Set
Percent change in 24-hour urinary oxalate:creatinine ratio to Month 6	MMRM	Full Analysis Set
Percent change in plasma oxalate from baseline to Month 6	MMRM	Plasma Oxalate Analysis Set
Proportion of Patients with 24-hour urinary oxalate ≤1.5xULN at Month 6	СМН	Full Analysis Set
Proportion of Patients with 24-hour urinary oxalate ≤ULN at Month 6	СМН	Full Analysis Set
Absolute change in plasma oxalate from baseline to Month 6	MMRM	Plasma Oxalate Analysis Set

^eGFR will be summarized descriptively (i.e. no formal testing) because this endpoint is not expected to change during the 6 months.

The following secondary endpoints which are assessed beyond Month 6 will be summarized to demonstrate long-term durability of lumasiran using the All Lumasiran Treated Set.

Descriptive statistics of percent change in 24-hour urinary oxalate at and after 6 months of lumasiran will be presented by treatment sequence (lumasiran/lumasiran, placebo/lumasiran) and the all treated arm (pooling treatment arms). A Wilcoxon-signed rank test (2-sided) will be conducted to test the null hypothesis of no change from baseline at selected timepoints (Months 6, 12, 18, 30, 36, 42 and 54). Additionally, the mean percent change from baseline with associated 95% (CIs) confidence intervals at each selected timepoint will also be presented. Supportive figures of mean (+/-standard error) percent change will be generated.

Descriptive statistics of percent change in 24-hour urinary oxalate will also be generated at visits during the entire study using the FAS set. Supportive figure of mean (+/- standard error) percent change will also be generated. An analysis of the percentage of time that 24-hour urinary oxalate level is at or below the near-normalization threshold will be summarized. A patient is considered to have met the threshold if the 24-hour urinary oxalate level is  $\leq 1.5 \text{xULN}$  at a post-baseline visit.

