For each patient, the percentage of time that 24-hour urinary oxalate level is at or below the near normalization threshold (ie,  $\leq 1.5 \text{xULN}$ ) will be calculated as follows:

$$\frac{cumulative\ months\ at\ or\ below\ near\ normalization\ threshold}{cumulative\ months\ of\ valid\ assessments}\times 100$$

where cumulative months at or below the near normalization will be defined as the summation across all intervals that met the threshold and cumulative months of valid assessments will be defined as the summation across all valid post-baseline collections.

Given that the sample collection varies during the study (e.g. monthly up until M9, every 3 months until M24, every 6 months until Month 60), the calculation will take into account the following considerations:

- Time will be restricted to a maximum of 36 months on lumasiran (that is, up to protocol defined month 36 visit for lumasiran/lumasiran arm or up to protocol defined month 42 visit for placebo/lumasiran arm) or premature treatment discontinuation, whichever occurs first.
- A linear interpolation method will be used for to determine the bookend dates at which the patient crossed into the threshold and crossed out of the threshold.

Descriptive statistics of percentage of time at or below the threshold (among the subset of patients who had at least one post-baseline value which met threshold) will be presented for each treatment sequence arm and the all treated arm. In addition, the number of patients and associated percentage of patients in each category (e.g. <25%,  $\ge25\%$  to <50%,  $\ge50\%$  to <75%,  $\ge75\%$  to 100%) will also be presented.

Descriptive statistics of eGFR at and after 6 months of lumasiran will be presented. Shift tables of eGFR categories from baseline to post-baseline visits and an overall worst post-baseline will also be generated.

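### Does a 1.5×ULN threshold of 0.771, just above the 0.70 entry floor, call for a separate analysis of patients already at threshold at baseline?

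*SAP*

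**What the plan says.** - Protocol 4.1, criterion 3 sets the entry floor: "Mean 24-hour urinary oxalate excretion from the first 2 valid 24-hour urine collections is ≥ 0.70" mmol/24h/1.73m².
- SAP Appendix A sets the ULN "for 24-hour urinary oxalate corrected for BSA is estimated to be 0.514" mmol/24hr/1.73m², from samples of 100 healthy adults run on the validated assay. SAP Section 8 explains that the value quoted before belonged to a different assay.
- SAP 5.6 places fourth among the tested secondary endpoints: "Proportion of patients with 24-hour urinary oxalate levels at or below 1.5xULN at Month 6".
- SAP 7.2 states that "the number and associated percent of patients who met each threshold at Month 6 will be presented by treatment arm". It adds a CMH test stratified at a baseline of 1.70, an odds ratio and a Newcombe interval. Neither threshold endpoint carries a condition on baseline.
- For the extension, SAP 7.2 states that the "percentage of time that 24-hour urinary oxalate level is at or below the near-normalization threshold will be summarized". Its descriptive statistics are taken "among the subset of patients who had at least one post-baseline value which met threshold" and are shown for each treatment sequence and pooled.
- SAP 5.4, for the double-blind period: "baseline will be defined as the median of all valid 24-hour urine PD parameters collected prior to the first dose date/time of study drug". For placebo patients who go on to lumasiran, "the baseline will be defined as the median of all valid assessments at month 6".

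**The concern.** A responder endpoint is usually read as patients brought to the target by treatment. Here 0.771 lies above the entry floor, so a patient can enter already at target, rise by 10% and still count. Three consequences would matter if such patients were common:

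- The placebo response rate in the fourth test would rise and the arm difference would shrink.
- The reported proportion would be harder to read as near-normalisation due to lumasiran.
- The percentage-of-time summary would credit lumasiran with time at a level that the patient already had. This applies especially to placebo patients re-baselined at Month 6, where no entry floor operates.

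SAP 7.2 plans neither a count of these patients nor an analysis without them. The sensitivity analyses (SAP 7.1.1) concern the primary endpoint only, and the baseline-oxalate subgroup cut (SAP 7.3) is at 1.70.

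**Working it through.** **Threshold against floor.** 1.5 × 0.514 = 0.771, and 0.771/0.70 − 1 = 10.1%. The ≤ULN endpoint has no such overlap at the floor: reaching 0.514 from 0.70 needs a fall of 1 − 0.514/0.70 = 26.6%.

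**Response assumptions.** These are the plan's own (Protocol 7.1, SAP 5.1): mean reduction 17% on placebo and 54% on lumasiran, SD 25. They reproduce the stated sample size. Placebo n = (1 + 1/2) × (25/37)² × (1.960 + 1.282)² = 7.2, rounded up to 8, plus 16 on lumasiran, makes 24. Power by the noncentral t is 90.4%, against 90% stated.

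**Baseline assumptions.** The documents give no distribution. I take a lognormal with distribution function F, truncated at 0.70, with median 1.5 or 2.0 and log-SD 0.3 or 0.4. A wider case (1.2, 0.5) is added as a stress test.

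- Band share = [F(0.771) − F(0.70)] / [1 − F(0.70)].
- P(at or below 0.771 at Month 6 | baseline b) = Φ{[100(0.771/b − 1) + m]/25}, with m = 17 or 54. This applies the same percent change at every baseline, which is a simplification.
- Rates average that probability over all baselines from 0.70, or over baselines above 0.771 only.

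| Median, log-SD | Band share | Expected of 30 | P(≥1 of 10 placebo) | Placebo rate, all / restricted (%) | Lumasiran rate, all / restricted (%) | Difference, all / restricted (points) |
|---|---|---|---|---|---|---|
| 1.5, 0.3 | 0.78% | 0.23 | 7.5% | 15.8 / 15.3 | 59.3 / 58.9 | 43.5 / 43.7 |
| 1.5, 0.4 | 2.03% | 0.61 | 18.5% | 17.6 / 16.3 | 58.4 / 57.5 | 40.8 / 41.2 |
| 2.0, 0.3 | 0.05% | 0.02 | 0.5% | 6.45 / 6.41 | 41.40 / 41.37 | 34.96 / 34.96 |
| 2.0, 0.4 | 0.43% | 0.13 | 4.2% | 8.5 / 8.2 | 42.8 / 42.5 | 34.2 / 34.3 |
| 1.2, 0.5 (stress) | 5.5% | 1.7 | 43% | 25.7 / 22.5 | 66.2 / 64.3 | 40.6 / 41.9 |

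The restriction moves the difference by at most 0.5 points in the four main cases and by 1.3 points in the stress case. In every case the difference with all patients included is no larger than the restricted one.

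**Month 6 re-baseline.** Under the same model, the expected number of 10 placebo patients at or below 0.771 before their first lumasiran dose is 1.6, 1.8, 0.6 and 0.9 in the four main cases. With zero mean placebo change it is 0.6, 0.8, 0.2 and 0.3. Patients whose original baseline lay between 0.70 and 0.771 contribute only 0.06, 0.16, 0.004 and 0.03 of these. The rest entered above 0.771 and fell while on placebo, which a slightly lower threshold would not prevent.

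**What the planned output already shows.** SAP 5.2 defines descriptive statistics to include quartiles, minimum and maximum. SAP 6.2 applies them to baseline 24-hour urinary oxalate, and Protocol 7.2.4 gives baseline summaries by arm and overall. If an arm's minimum exceeds 0.771, the count there is zero. If it does not, the patient listings supply the count. For placebo patients the listings carry both baselines (SAP 5.2).

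**The case for a change.** The strongest case for a change has four parts.

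1. **Small numbers make one patient visible.** With about 10 on placebo, one patient is 10 percentage points. Under the plan's placebo figures, a placebo patient starting between 0.70 and 0.771 has a 75% to 86% chance of counting as a responder. The analysis baseline is a median of all valid collections while eligibility uses a mean of two, so it can even fall below 0.70. All of this stands. But most likely the band holds no placebo patient at all, and if it holds one, the listings show it.

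2. **The sponsor already restricts by baseline elsewhere.** Plasma oxalate endpoints exclude patients near the assay's quantification limit (SAP 7.2). That exclusion answers a different problem, namely that a reduction below the limit cannot be measured. A patient in the urinary band can still fall measurably, and that fall enters the percent-change and absolute-change analyses.

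3. **Protocol 1.2.2 uses near-normal for values under 0.70, while the SAP's near-normal limit is 0.771.** The labels do differ. The protocol text is background on another study and does not define the endpoint; SAP 7.2 and Appendix A do.

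4. **The percentage-of-time summary is uncontrolled and limited to patients who met the threshold at least once.** This is the best part of the case, because randomisation does not protect that summary. It is descriptive, however, and the re-baselined patients have their own treatment-sequence column. Lumasiran/lumasiran patients, about two thirds of the total, are not re-baselined. Only the pooled column mixes the two groups.

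In favour of prespecification, a count fixed in advance is cleaner than one made afterwards. That is true but carries little weight: the cut is fixed by 1.5×ULN, so there is no analyst's choice to guard against.

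**Conclusion.** The arithmetic and the absence of a planned separation both hold, but the plan is sound as written. The fourth test compares randomised arms on a level reached, so patients already at the level do not invalidate it. Chance could place such a patient in either arm, and the test allows for that. The expected effect is a slightly smaller difference: at most 0.5 points in the main cases, from 0.02 to 0.6 of 30 patients. A restricted analysis would most likely drop nobody, or one patient, and repeat the main table.

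The reading of the responder rate does not rest on this endpoint alone. The primary endpoint is percent change, the first secondary test is absolute change, and the ≤ULN test requires a fall of at least 26.6% from the entry floor. A patient who merely stays between 0.70 and 0.771 shows no benefit on any of them.

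The size rests on assumed baseline distributions, since the documents give none. A population much closer to the floor than the stress case would raise the count but would not affect the test's validity. A count of patients at or below 0.771 at baseline can be read from planned output if a reader of the report asks for it.
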